13.0 Non-Study Treatments

13.1 Prior and Concomitant Medications

All medications (including prescription and over-the-counter medications, supplements, and herbal products) taken from 28 days before Baseline (Day 1) through the TOC visit will be recorded on the eCRF. Only the use of antifungal medications, antibiotics for any reason or medications to treat an AE will be recorded after the TOC visit through the last study visit (FU). Start and stop dates of concomitant medications taken during antifungal therapy will be recorded on the eCRF. Prior and concomitant medications will be reviewed and recorded at all study visits.

Certain concomitant medications must be administered with caution or close monitoring as described in Appendix A [Section 21.0](#).

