18.7 Efficacy

18.7.1 Efficacy Assessments

The primary efficacy endpoint of the study is the percentage of subjects with clinical cure (complete resolution of signs and symptoms) at the TOC visit. Secondary efficacy endpoints include the percentage of subjects with mycological eradication (negative fungal culture) at the TOC visit, the percentage of subjects with both clinical cure and mycological eradication at the TOC and FU visits, the percentage of subjects with continued clinical

response (continued absence of signs and symptoms) at the FU visit and the time to resolution of signs and symptoms after initiation of study drug. The percentage of subjects with a negative KOH test at the TOC visit, the percentage of subjects who are free of signs and symptoms at the FU visit, the percentage of subjects by *Candida* species infection at Baseline, the percentage of isolates susceptible to SCY-078 and fluconazole, the percentage of subjects with clinical cure (complete resolution of signs and symptoms) at TOC by *Candida* species and the percentage of subjects with mycological eradication (negative fungal culture) at TOC by *Candida* species will be evaluated as exploratory endpoints.

The following treatment outcome definitions will be used for the assessment of efficacy:

Clinical Outcome

- **Clinical cure:** Complete resolution of signs and symptoms of vulvovaginal infection without need for further antifungal treatment. Specifically, for complete resolution, any sign or symptom should be absent (score = 0) by the TOC visit.
- **Clinical failure:** No response to therapy or incomplete resolution of signs and symptoms or need for additional vulvovaginal or systemic antifungal therapy. If the subject receives or self-administers topical drug therapy for the treatment of vulvovaginal irritation/pruritus such as topical analgesic or corticosteroid after completing treatment with the study drug and before the TOC visit, the subject is considered a clinical failure.
- **Continued Clinical Response:** Continued absence of signs and symptoms of vulvovaginal infection at the FU visit in subjects who achieved clinical cure at the TOC visit.
- **Free of Signs and Symptoms:** Absence of signs and symptoms of vulvovaginal infection at the FU visit.
- **Mycological Outcome**
- **Mycological eradication:** A subject with negative culture (no growth) for *Candida* species.
- **Mycological persistence:** A subject with a positive culture for *Candida* species.

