11.8 Efficacy Endpoints

11.8.1 Primary Efficacy Endpoint

The primary efficacy endpoint is the percentage of subjects with Clinical Cure at the TOC visit.

Clinical Cure is defined as complete resolution of signs and symptoms of vulvovaginal infection without need for further antifungal treatment. Specifically, for complete resolution, any sign or symptom should be absent (score = 0) by the TOC visit. If any sign or symptom is missing, the subject's Clinical Cure status will be considered as missing.

Conversely, Clinical Failure is defined as no response to therapy or incomplete resolution of signs and symptoms or need for additional vulvovaginal or systemic antifungal therapy. If the subject receives or self-administers topical drug therapy for the treatment of vulvovaginal irritation/pruritus such as topical analgesic or corticosteroid after completing treatment with the study drug and before the TOC visit, the subject is considered a clinical failure.

The signs (edema, erythema and excoriation or fissures) and symptoms (itching, burning and irritation) of infection will be assessed by the investigator and the subject, respectively, on the VSS Scale. The VSS Scale is a standardized, predefined scale where each sign and symptom will

be given a numerical rating based on severity (absent = 0; mild = 1; moderate = 2; severe = 3) to calculate a total composite score.

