11.8.2 Secondary Efficacy Endpoints

The secondary efficacy endpoints include the following:

- The percentage of subjects with Mycological Eradication (negative fungal culture) at the TOC and FU visit.

Mycological Eradication is defined as a subject with negative culture (no growth) for *Candida* species. Conversely, Mycological Persistence is defined as a subject with positive culture for *Candida* species.

- The percentage of subjects with both Clinical Cure and Mycological Eradication at the TOC visit. If either component assessment is missing, the subject will be considered as missing for this endpoint and imputed as non-responders in the analysis
- The percentage of subjects with both absence of signs and symptoms and Mycological Eradication at the FU visit. If either component assessment is missing, the subject will be considered as missing for this endpoint and imputed as non-responders in the analysis
- The percentage of subjects with Continued Clinical Response at the Follow-up (FU) visit, defined as continued absence of signs and symptoms in subjects who achieved Clinical Cure at the TOC visit
- The time to resolution of signs and symptoms after initiation of study drug, defined as time (days) from first dose of study medication to the first resolution of signs and symptoms. Subjects who discontinued early will be censored at the last available assessment.

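### Time to resolution and Mycological Eradication credit clearance after non-study antifungal therapy to the randomised arm, which biases the secondary comparisons, probably but not necessarily towards no difference

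*SAP*

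**What the plan says.** **Time to resolution (SAP 11.8.2)** is "defined as time (days) from first dose of study medication to the first resolution of signs and symptoms". The event is not capped at TOC and carries no condition on other treatment. The only censoring rule is "Subjects who discontinued early will be censored at the last available assessment". SAP 11.9.2 analyses it by Kaplan-Meier with pairwise log-rank tests against fluconazole.

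**Mycological Eradication (SAP 11.8.2, at TOC and FU)** is "defined as a subject with negative culture (no growth) for" *Candida* species, again with no condition on other treatment. Protocol 18.7.1 has the same culture-only definition.

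**The primary endpoint differs.** SAP 11.8.1 includes "need for additional vulvovaginal or systemic antifungal therapy" among the grounds for Clinical Failure, as does Protocol 18.7.1. It also fails a subject who uses topical symptomatic treatment after completing study drug and before TOC.

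**Related rules:**
- Protocol Appendix A prohibits any antifungal other than study drug during the study. Such use is not among the discontinuation reasons in Protocol 11.3.
- Protocol 13.1 records all medications through TOC. From then to FU, "Only the use of antifungal medications, antibiotics for any reason or medications to treat an AE will be recorded after the TOC visit".
- SAP 7 makes mITT the primary efficacy population. It gives interfering concomitant medication as an example of a major deviation that excludes a subject from PP.
- SAP 8 assigns failure only where the TOC or FU value is missing.

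**The concern.** Signs are rated after dosing only at TOC, FU and unscheduled visits (Protocol 14.10), so FU is one of just two scheduled points at which full resolution can be established. Take a subject who fails at TOC, receives a non-study antifungal, stays in the study and scores 0 throughout at FU. She has not discontinued and has no missing value, so under SAP 11.8.2 she is a resolution event for her randomised arm. Likewise, a subject treated before the TOC sample can be a Clinical Failure and a mycological success because of the same treatment. The SAP does not remark on the difference.

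The primary objective is to choose a dose by comparing regimens, and these endpoints inform that choice. If clearance produced by another antifungal is credited to a regimen, the secondary comparisons no longer describe what the study drug did.

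**Working it through.** The plan has no figure to reproduce: no formal sample size calculation was done, and 6 × 30 = 180 is simply the allocation. All rates below are assumptions; only the 30 per arm comes from the documents. "Treated" is not used as a quoted term here: it means given a non-study antifungal.

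**1. Which endpoints carry a condition on antifungal therapy?**
- Clinical Cure at TOC: yes, through the Clinical Failure rule.
- "The percentage of subjects with both Clinical Cure and Mycological Eradication at the TOC visit": yes, inherited from Clinical Cure.
- Time to resolution: no.
- Eradication at TOC and FU, and negative KOH at TOC: no.
- FU composite: no. It uses absence of signs and symptoms, not Clinical Cure.
- Free of signs and symptoms at FU, and Continued Clinical Response: no explicit condition.

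**2. Time to resolution: share resolved by FU.**

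Share = TOC share + failures × (treated × clearing if treated + untreated × 10%).
- As written, 60% treated and 80% clearing: 0.50 + 0.50 × (0.48 + 0.04) = 76%; 0.70 + 0.30 × 0.52 = 86%.
- As written, 80% treated and 85% clearing: 0.50 + 0.50 × (0.68 + 0.02) = 85%; 0.70 + 0.30 × 0.70 = 91%.
- Treated kept unresolved: 0.50 + 0.50 × 0.04 = 52% and 0.70 + 0.30 × 0.04 = 71%; or, with 0.02 in place of 0.04, 51% and 71%.

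The gap at FU is 6-10 points as written and 19-20 points with treated subjects kept unresolved. At lower treatment rates (80% clearing) the gap is 20 × (1 − share of failures clearing):
- 10% treated: 20 × (1 − 0.17) = 16.6 points, against 20 × (1 − 0.09) = 18.2.
- 30% treated: 20 × (1 − 0.31) = 13.8 points, against 20 × (1 − 0.07) = 18.6.

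**3. Expected log-rank Z with two event times (TOC, FU).**

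U = Σ(d₂ − d·r₂/r); V = Σ d(r₁/r)(r₂/r)(r − d)/(r − 1).
- TOC, 50% vs 70%: d = 15 + 21 = 36, so U = 21 − 18 = 3 and V = 36 × 0.25 × 24/59 = 3.66.
- FU, 15 and 9 at risk: the same share clears in each arm, so U gains nothing. V gains 1.47 or 1.23 as written, and 0.23 or 0.12 with treated subjects kept unresolved.
- As written: Z = 3/√5.13 = 1.33 to 3/√4.89 = 1.36. Kept unresolved: 3/√3.89 = 1.52 to 3/√3.78 = 1.54.

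At 50% vs 80%, Z is 2.10-2.14 as written against 2.36-2.39, an approximate power of 56% against 66%. In both cases the gap at TOC is untouched; the late events add variance and no signal.

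**4. Direction: eradication.**

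Observed rate p′ = p + (1 − p)·r·e, where p is eradication on drug, r the share of failures treated before the sample and e eradication after treatment. Take 70% vs 55% (15.0 points) and e = 0.8.
- Equal r: the difference shrinks by the factor (1 − r·e). For r = 10/20/40% it is 13.8/12.6/10.2 points, and power at 30 per arm is 20/18/14% against 22%.
- r = 10% vs 30% (more in the worse arm): 72.4% − 65.8% = 6.6 points.
- r = 30% vs 10% (more in the better arm): 77.2% − 58.6% = 18.6 points.
- No true difference (55% each), r = 30% vs 10%: 65.8% − 58.6% = 7.2 points.

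**5. Direction: time to resolution.**

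This is a simulation of 40,000 per arm with exponential resolution to Day 10, 60% vs 50% resolved, and 80% of treated failures clear at Day 25. The hazard ratio is about 1.30 with treated subjects as non-events. As written it is 1.22 (50%/50% of failures treated), 1.05 (30%/60%) or 1.44 (60%/30%). With equal arms and 50%/10% treated it is 1.29 instead of 1.00.

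**The case against.** - **Prohibition and deviation.** Non-study antifungals are prohibited, so each case is a deviation and may be rare. This stands as a limit on size. But the plan expects some use: it builds Clinical Failure partly on it and records it through FU.
- **Existing safeguards.** The secondary endpoints are also analysed in PP, which may exclude these subjects, and the TOC composite already fails them. This stands, but mITT and ITT keep them, and the FU composite does not fail them.
- **Withdrawal.** A treated subject who also withdraws while unresolved is censored, so not every treated failure becomes an event. This stands; step 2 assumes all of them stay to FU.
- **Definition.** Scoring the culture as observed is a legitimate treatment-policy choice and is the protocol's own definition. A reader might infer that the SAP has departed from the protocol here; it has not. What is missing is any stated reason for handling the same therapy in opposite ways.
- **Direction.** A reader might infer that the gap must pull the arms together. The documents give no rates of antifungal use by arm, and steps 4 and 5 show that a difference can also widen or appear.
- **Transfer to eradication at TOC.** The 60-80% treated in step 2 cannot be carried over. Only use before the TOC sample counts (SAP 10.4 window, study days 8 to 13), and no on-site visit is scheduled between Day 3 and TOC.

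**Conclusion.** The gap holds on the text. Followed as written, SAP 11.8.2 counts clearance or a negative culture after non-study antifungal therapy as success in mITT and ITT. The resulting bias probably narrows differences, because weaker arms have more failures to treat. That direction is likely, not certain, since it depends on how often failures are treated in each arm.

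On the assumed rates the distortion is marked at the FU end of the curve (6-10 points against 19-20) and moderate for the log-rank test (Z about 1.34 against 1.53). It is smaller for eradication at TOC.

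A reader might infer that a weak regimen would look like the best one throughout, or that the primary result is compromised. Neither follows: the Kaplan-Meier gap at TOC is unchanged, and Clinical Cure already handles this therapy. The consequence is confined to secondary and exploratory endpoints of a study not powered for formal comparisons.

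**What to change.** Amend SAP 11.8.2 and 11.8.3 before unblinding; SAP 12 gives later changes unblinded, exploratory status. This concerns scoring only, not which treatment subjects may receive.

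1. **Time to resolution.** A subject who starts non-study systemic or vaginal antifungal therapy before resolution has no event thereafter. She is carried as unresolved to her last planned assessment, not censored when that therapy starts, since censoring there would treat its start as uninformative. Apply the same to topical symptomatic therapy only up to TOC. After TOC such use is not systematically recorded (Protocol 13.1).
2. **Binary endpoints.** For Mycological Eradication at TOC and FU, negative KOH at TOC, absence of signs and symptoms at FU, the FU composite and Continued Clinical Response, a subject who received non-study systemic or vaginal antifungal therapy between first dose and that assessment is a non-responder, in line with the Clinical Failure rule.
3. **Supportive output.** Show as-observed results alongside, and tabulate such therapy by arm so that the direction of any bias can be judged.

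Cost: SAP wording and one derivation from medication data already collected. Reported rates become somewhat lower, and SAP 12 must record the added condition as a change from the protocol's culture-only definition.

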11.8.3 Exploratory Efficacy Endpoints

The exploratory efficacy endpoints include the following:

- Percentage of subjects with a negative KOH test at the TOC visit
- Percentage of subjects who are free of signs and symptoms at the FU visit
- Percentage of subjects by *Candida* species infection at Baseline
- Percentage of isolates susceptible to SCY-078 and fluconazole at the TOC and FU visits
- Percentage of subjects with clinical cure at TOC by *Candida* species at Baseline
- Percentage of subjects with mycological eradication at TOC by *Candida* species at Baseline

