9.3 Exploratory Endpoints

- Percentage of subjects with a negative KOH test at the TOC visit
- Percentage of subjects who are free of signs and symptoms at the FU visit
- Percentage of subjects by *Candida* species infection at Baseline
- Percentage of isolates susceptible to SCY-078 and fluconazole
- Percentage of subjects with clinical cure (complete resolution of signs and symptoms) at TOC by *Candida* species
- Percentage of subjects with mycological eradication (negative fungal culture) at TOC by *Candida* species
- Determination of the PK parameters (C_{max} and AUC) for each dosing regimen and evaluation of the dose/exposure relationship relative to clinical outcome

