10.1.2 Study Assessments

The study will include efficacy, safety and PK assessments.

Efficacy Assessments

Treatment outcome will be assessed primarily based on clinical cure (complete resolution of signs and symptoms) at the TOC (Day 10) visit. Secondary efficacy endpoints will include mycological eradication (negative fungal culture) at the TOC visit, a composite endpoint of both clinical cure and mycological eradication at the TOC and FU visits, continued clinical response (continued absence of signs and symptoms) at the FU visit and time to resolution of signs and symptoms after initiation of study drug. Additionally, the percentage of subjects with a negative KOH test at the TOC visit, the percentage of subjects who are free of signs and symptoms at the FU visit, the percentage of subjects by *Candida* species infection at Baseline, the percentage of isolates susceptible to SCY-078 and fluconazole will be explored, the percentage of subjects with clinical cure (complete resolution of signs and symptoms) at TOC by *Candida* species and the percentage of subjects with mycological eradication (negative fungal culture) at TOC by *Candida* species will be evaluated as exploratory efficacy endpoints.

Clinical Evaluation

The signs (edema, erythema and excoriation or fissures) and symptoms (itching, burning and irritation) of infection will be assessed by the investigator and the subject, respectively, on the VSS Scale [provided in [Appendix B](#)]). The VSS Scale is a standardized, predefined scale where each sign and symptom will be given a numerical rating based on severity (absent = 0; mild = 1; moderate = 2; severe = 3) to calculate a total composite score.

Mycological Testing

Mycological tests will include direct microscopic examination with 10% KOH and fungal cultures. KOH will be performed locally at Screening for the determination of subject eligibility and at the TOC and FU visits for the exploratory assessment of treatment outcome. Fungal cultures will be performed centrally at Screening for species identification and susceptibility testing and at the TOC and FU visits for the assessment of treatment outcome and susceptibility testing for subjects with positive cultures.

Pharmacokinetic Assessments

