14.9 Vulvovaginal Samples for KOH and Fungal Culture

At Screening, a vulvovaginal specimen will be obtained for direct microscopic examination with 10% KOH. Subjects must have a positive KOH test at Screening to be randomized to one of the study treatment groups. The Screening KOH will be assessed at the site by the investigator or designee. A vaginal sample will also be obtained at Screening for fungal culture and species identification by the central laboratory and for susceptibility testing against SCY-078, fluconazole and additional antifungal agents. Central susceptibility testing will be done as per CLSI M27-A3 guidelines. An additional vulvovaginal specimen will be collected at the TOC and FU visits for local KOH testing and for fungal culture by the central laboratory for treatment outcome assessment. In addition, susceptibility testing will be done at the central laboratory for all positive cultures for *Candida* spp. Vulvovaginal samples may also be taken at unscheduled visits, if needed.

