2. STUDY OBJECTIVES

Primary Objective:

- To identify the recommended dose of oral SCY-078 in subjects with moderate to severe Acute Vulvovaginal Candidiasis (AVVC) by comparing the efficacy of different dose levels and dosing regimens of oral SCY-078

Secondary Objectives:

- To evaluate the efficacy of oral SCY-078 in subjects with AVVC based on mycological and clinical outcomes
- To evaluate the safety and tolerability of different dose levels and dosing regimens of oral SCY-078 in subjects with AVVC

Exploratory Objectives:

- To explore the efficacy of SCY-078 in subjects with AVVC based on potassium hydroxide (KOH) testing at the TOC visit
- To explore the efficacy of SCY-078 in subjects with AVVC based on additional clinical outcomes
- To explore the prevalence of Candida species among subjects with AVVC
- To explore the in vitro activity of SCY-078 against baseline Candida spp. isolates
- To explore clinical and mycological outcomes by Candida species
- To evaluate the PK of SCY-078 after oral administration of different dose levels and dosing regimens of SCY-078 in subjects with AVVC

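### The SAP limits the susceptibility endpoint to TOC and FU isolates, so the objective about baseline Candida isolates has no stated analysis

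*SAP*

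**What the plan says.** The exploratory objective in SAP section 2, repeated in Protocol 8.3, is "To explore the in vitro activity of SCY-078 against baseline Candida spp. isolates". The matching protocol endpoint (9.3) is "Percentage of isolates susceptible to SCY-078 and fluconazole", with no visit attached. SAP 11.8.3 turns this into "Percentage of isolates susceptible to SCY-078 and fluconazole at the TOC and FU visits".

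The baseline data will exist. Protocol 14.9 has the Screening sample sent to the central laboratory for culture, species identification and "for susceptibility testing against SCY-078, fluconazole and additional antifungal agents". Later isolates are tested as well: Protocol 10.1.2 has cultures done "at the TOC and FU visits for the assessment of treatment outcome and susceptibility testing for subjects with positive cultures".

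Three other bullets in SAP 11.8.3 name Baseline, but all three concern species: its distribution, and clinical and mycological outcome by baseline species. SAP section 12 declares no material departure from the protocol and gives any analysis not specified in the SAP the status of an unblinded, exploratory investigation.

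**The concern.** A programmer following SAP 11.8.3 would tabulate susceptibility at TOC and FU and stop there, and the objective that names baseline isolates would go unanswered. A baseline table added after unblinding would carry the post hoc label of SAP section 12, although it answers an objective stated in advance.

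The isolates that are tabulated also form a selected set. A subject supplies one only if her culture is positive at that visit, which depends on the treatment and possibly on the organism's susceptibility. SAP 11.9.3 sends exploratory endpoints through the same tests as the primary and secondary endpoints and makes only the species subgroups descriptive. Read literally, that puts between-arm tests on a set of isolates selected after randomization.

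The subject matters to the programme. Protocol 7.1 gives fluconazole resistance and less susceptible species as part of the case for a new drug, and susceptibility at baseline is the direct evidence on that point.

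**Working it through.** The documents state no susceptibility percentage and no expected isolate count, so there is no figure of the plan's to reproduce beyond 180 / 6 = 30 per group. The check compares the texts and then uses arithmetic on assumed rates.

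**1. Text comparison.** Objective: baseline isolates (SAP 2, Protocol 8.3). Protocol endpoint: no visit limit (9.3). Data: Screening, TOC and FU isolates all tested (Protocol 10.1.2, 14.9). SAP endpoint: TOC and FU only (11.8.3). The Screening sample precedes the first dose, so it meets the SAP's definition of Baseline (10.3). The one visit named in the objective is missing from the SAP endpoint.

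**2. Who supplies a TOC or FU isolate.** Under SAP 11.8.2, "Mycological Persistence is defined as a subject with positive culture for" Candida species. That is a mycological state. SAP 11.8.1 says "Clinical Cure is defined as complete resolution of signs and symptoms of vulvovaginal infection without need for further antifungal treatment", with no culture component, so a clinically cured subject can supply a TOC isolate. A subject who is culture-negative at TOC can supply an FU isolate. A subject with a missing culture is counted as mycologically positive under SAP section 8 but supplies no isolate. The accurate description is culture-positive at that visit.

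**3. Denominators.** Assume 70% to 100% of randomized subjects are culture-positive at baseline (entry requires a positive KOH test, not a positive culture) and 20% to 45% of those are still positive at TOC.
- Baseline: 180 × 0.70 = 126 to 180 × 1.00 = 180 isolates, or 21 to 30 per group.
- TOC: 126 × 0.20 = 25 to 180 × 0.45 = 81 isolates, or about 4 to 14 per group.

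**4. How far the TOC percentage can move from baseline.** Let s be the susceptible share at baseline, and pS and pR the probabilities of a positive TOC culture for susceptible and non-susceptible baseline isolates. Then

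TOC susceptible share = s·pS / [s·pS + (1 − s)·pR].

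All three inputs are assumptions. Example with s = 0.90, pS = 0.3, pR = 0.5: 0.27 / (0.27 + 0.05) = 84.4%, a shift of −5.6 points. The grid, with shifts in points:

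| s | 0.4 / 0.4 | 0.3 / 0.5 | 0.3 / 0.7 | 0.2 / 0.8 |
|---|---|---|---|---|
| 80% | 80.0% (0) | 70.6% (−9.4) | 63.2% (−16.8) | 50.0% (−30.0) |
| 90% | 90.0% (0) | 84.4% (−5.6) | 79.4% (−10.6) | 69.2% (−20.8) |
| 95% | 95.0% (0) | 91.9% (−3.1) | 89.1% (−5.9) | 82.6% (−12.4) |

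Columns are pS / pR. When the two are equal, the shift is zero.

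**5. Why between-arm tests fail on these isolates.** Assume 8% fluconazole-non-susceptible isolates at baseline in every arm. In the fluconazole arm, let susceptible isolates persist in 40% of subjects and non-susceptible ones in 90%. In the SCY-078 arms, let 40% persist regardless of fluconazole susceptibility.
- Fluconazole arm at TOC: 0.08 × 0.9 / (0.08 × 0.9 + 0.92 × 0.4) = 0.072 / 0.440 = 16.4% non-susceptible.
- Each SCY-078 arm at TOC: 0.032 / 0.400 = 8.0%.
- Six arms pooled: (0.072 + 5 × 0.032) / (0.440 + 5 × 0.400) = 0.232 / 2.44 = 9.5%.

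The arms were identical at baseline and no organism changed. The gap between 16.4% and 8.0% comes entirely from which subjects still had an isolate to test.

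**The case against.** The best defence has four parts.

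- **The plan may already cover it.** The SAP says it does not repeat every protocol definition, its design section keeps susceptibility testing of positive Screening cultures, and its section 15 outline of tables and listings is only a heading in the text available. A baseline susceptibility table there cannot be excluded. This lowers confidence, but such a table would still conflict with the endpoint definition in 11.8.3.
- **TOC and FU susceptibility is worth reporting.** The protocol plans to test those isolates, and a percentage of TOC isolates correctly describes TOC isolates. This stands: those summaries need not be removed or reduced to a listing.
- **A reader might infer that these isolates exist only in treatment failures and that the percentages are therefore biased.** The documents do not support that. Clinical cure has no culture component, and bias arises only if the figure is read as baseline susceptibility and persistence depends on susceptibility.
- **A reader might also infer that TOC non-susceptibility would be roughly double the baseline value.** Assumed eradication of 60% against 10%, or 70% against 30%, does give 10.6% to 29.2% at TOC for 5% to 15% at baseline. But the persistence ratios behind those pairs are 0.9 / 0.4 = 2.25 and 0.7 / 0.3 = 2.33, so the doubling is built in. Those ratios suit at most the single fluconazole arm. Protocol 7.1 reports that SCY-078 keeps its activity against more than 90% of azole-resistant strains, and the pooled figure in the working is 9.5% against 8%.

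**Conclusion.** The mismatch is real and can be read directly from the text: the objective names baseline isolates, the data to meet it are collected, and the SAP endpoint leaves them out without declaring a change. TOC and FU isolates cannot replace them. They are fewer, they are selected by outcome, and the selection can differ by treatment, so they do not support between-arm tests either.

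The size of any difference between TOC and baseline susceptibility is unknown. Across the assumed inputs it runs from 0 to −30 points, and the documents give no basis for choosing a value in that range. The isolate counts also rest on assumed culture rates.

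The consequence is limited. This is one exploratory endpoint in a study that performed no formal sample size calculation, and the primary, secondary and safety conclusions do not depend on it. The baseline results will be in the database whatever the SAP says; what is at stake is whether their analysis is specified before unblinding.

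**What to change.** In SAP 11.8.3, add Baseline to the endpoint: the percentage of Baseline isolates susceptible to SCY-078 and to fluconazole, among all subjects with a positive baseline culture. Keep the TOC and FU percentages as separate descriptive summaries, shown alongside each subject's baseline isolate. In 11.9.3, extend the descriptive-only rule from the species subgroups to susceptibility, so that no between-arm test is run on TOC or FU isolates. Check the section 15 outline for a matching table.

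The text available cites a testing method but no cut-off for calling an isolate susceptible to SCY-078. The endpoint needs one at any visit, so state it at the same time or say that the MIC distribution will be reported instead.

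The cost is SAP wording and one table. No new samples or tests are needed, and the change should be made before unblinding.
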